Minimization of perioperative discomfort and complications, such as increased blood loss and length of hospital stay is a mutual goal amongst both patients and surgeons alike. To our knowledge, there have been no studies in the US and only one small study in Europe comparing the efficacy of tranexamic acid (TXA) and εaminocaproic acid (EACA or ACA, Amicar®) in TKA and total hip arthroplasty (THA). A double blind, randomized and placebo controlled trial in Spain involving 127 patients sorted into three different arms found that there was significant reduction of blood transfusions in the TKA and Amicar arms, and also less of a reduction in hemoglobin levels by post-op day 5.1 There were no statistical significance in the 35 patients administered TXA compared to the 32 patients administered EACA, and authors noted that the limited number of patients may have prevented any findings. Given the potency of TXA, it may in fact be more efficacious than Amicar, leading to improved patient outcomes. Despite the clinical advantages to using TXA vs. placebo, it is frequently felt to be financially prohibitive. TXA currently costs between \$100-200 per each IV dose. A unit of RBC costs between \$500-1000 dollars. A recent study comparing the cost of TKAs using TXA vs. those that did not found that although the pharmacy cost increased by \$140, the total hospital cost was decreased by about \$900 (looking at OR, blood, and total costs associated with admission).2 Amicar is significantly less expensive than TXA, and given its theoretically similar mechanism of action, is used as the agent of choice in many hospitals in the United States. Currently TXA is being used at Duke University for total joint arthroplasty. There are limited data comparing the clinical efficacy and cost effectiveness of the two anti-fibrinolytics. Given the increased potency of TXA, it may be more efficacious and ultimately more cost effective than Amicar. The primary objective of this study is to determine the effectiveness of TXA vs. Amicar by determining the percentage of patients requiring transfusions and blood loss in total joint arthroplasty. A secondary objective is to determine the overall cost of hospitalization when the two different products are used. We hypothesize that that TXA will decrease the transfusion rate in patients as compared to Amicar. We also hypothesize that the overall cost of hospitalization will be less in patients with TXA, despite the increased pharmacy cost.

3. Background Information

Hemostasis is an essential part of any surgical procedure, and especially in the case of total joint surgical procedures. Hemostasis is achieved through the steps of vasospasm, platelet adhesion, contact phase, and then fibrinolysis. Increased fibrinolysis can lead to increased intra-operative blood loss.³ Tourniquets during surgical procedures, such as the ones used during Total Knee Arthroplasty (TKA), have been shown to increase fibrinolysis during deflation, despite there being no change in circulating clotting factors.⁴ Medications that either retard or stop fibrinolysis potentially would decrease the breakdown of a clot leading to decreased operative blood loss while not impacting the risk of systemic thrombosis.⁵

Currently there are three FDA-approved antifibrinolytic agents. Approximin is currently not being used in the US market as a study in 2007 suggested that there might be an increased mortality associated with its use during cardiac surgery.⁵ While that conclusion was based largely on observational studies, A Cochrane review published in 2011 and a meta-analysis in 2012 concluded, regardless of the questionable increased risk caused by aprotinin, ε-aminocaproic acid tranexamic acid are safer in terms of risk of death and myocardial infarction than aprotinin.6-8 These lysine analogues have also been used to control non-surgical bleeding control such as the use of Amicar in thrombocytopenia and TXA in the treatment of uterine bleeding.^{9,10} Amicar and TXA are currently approved for nonsurgical settings of excessive bleeding where fibrinolysis is a contributing factor, like ocular bleeding, menorrhagia, cirrhosis, and placental abruption. Both of these agents are reversible competitive inhibitors of plasminogen/plasmin and are widely used in the fields of orthopaedics, cardiothoracic surgery, and transplantation to reduce blood loss. Amicar was the first agent to be used in hopes of reducing blood loss during major surgery, however shift began due to a worldwide shortage of Amicar. Although this shortage has since been corrected, TXA began being used as a result and is showing early promising results. TXA is 6-10 times more potent but has a similar toxicity profile.⁵ Amicar continues to still be widely used in cardiac surgery.

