Subject or *their* insurance provider will be responsible for all costs related to your medical care, including the drugs used in this study.

No direct monetary compensation will be offered for inclusion in the proposed study.

12. Data Analysis & Statistical Considerations

Subject characteristics and study results including those outlined above (considered complications or adverse events) will be recorded. ¹ The primary endpoint for this study is the percentage of patients requiring transfusions. The secondary endpoint include total blood loss (recorded as estimated blood loss intraoperatively as determined by anesthesia staff, and postoperatively recorded by nurses from the output in drains), change in hemoglobin (preoperative vs. postoperative hemoglobin that is routinely measured before discharge), and the total cost of hospitalization as billed by Duke University (including pharmacy cost, price each night in hospitalization, all other charges incurred during admission). Binary variable results will be compared using chi-square and Fisher's exact tests (where appropriate). We plan a comparison of continuous variable results using Wilcoxon rank sum and t-tests (where appropriate). We will consider multivariable logistic regression in determination of TXA and Amicar and their correlation with the above listed complications and adverse events. Anesthetic techniques will be recorded for analysis and covariate analysis will be performed at the end of the study. In order to perform a cost analysis, total cost of hospitalization including pharmacy cost, potential transfusion costs, and cost of stay. Based on the one small European study, sample size for finding the difference between two proportions was calculated using a proportion of 0.125 patients given Amicar were transfused (n=32 vs. 0.028 (n=35) given TXA. Using an alpha value of .05 and power of .90 it was determined that there would need to be 154 patients in each sample size to find a significant difference in independent samples. Our goal of enrolling 400 patients total (200 in each arm) will therefore be appropriate for this study

13. Data & Safety Monitoring

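### Does naming blood loss in the primary objective leave the primary endpoint undecided?

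*Combined protocol and SAP*

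**What the plan says.** The opening section (before section 3, Background Information) sets the primary objective as judging the effectiveness of TXA against Amicar by "determining the percentage of patients requiring transfusions and blood loss in total joint arthroplasty". The next sentence reads "A secondary objective is to determine the overall cost of hospitalization when the two different products are used", so blood loss is not placed among the secondary objectives there. The efficacy hypothesis in the same section concerns transfusion only: "We hypothesize that that TXA will decrease the transfusion rate in patients as compared to Amicar".

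Section 12 (Data Analysis & Statistical Considerations) assigns the endpoints: "The primary endpoint for this study is the percentage of patients requiring transfusions", and then "The secondary endpoint include total blood loss", along with change in hemoglobin and total cost of hospitalization. The sample size in that section is built on a "proportion of 0.125 patients given Amicar were transfused (n=32 vs. 0.028 (n=35) given TXA", "Using an alpha value of .05 and power of .90", and arrives at 154 per arm. The enrolment goal is 200 per arm.

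**The concern.** Read alone, the objective sentence gives transfusion and blood loss equal standing, while section 12 puts one above the other. The two outcomes can disagree. Transfusion is planned as an uncommon yes/no event (12.5% against 2.8%). Blood loss is a continuous measure and could reach significance when transfusion does not. In that event the objective sentence might be used to claim that the primary objective was met on blood loss. The plan has no multiplicity rule for two primary outcomes, so a claim allowed on either one would carry more than the nominal 5% error.

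**Working it through.** **Which outcome the plan treats as primary.** Four statements bear on this.

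| Place | Transfusion | Blood loss |
|---|---|---|
| Opening section, primary objective | named | named |
| Opening section, efficacy hypothesis | named | absent |
| Section 12, endpoints | primary | secondary |
| Section 12, sample size | sole basis | absent |

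Three of the four point to transfusion alone. The objective sentence is the outlier. It designates no endpoint and attaches no test to blood loss.

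**Does the sample size confirm this?** Inputs from section 12: p1 = 0.125 (Amicar), p2 = 0.028 (TXA), alpha 0.05, power 0.90. Sidedness is not stated; two-sided is assumed, so the normal quantiles are 1.960 and 1.2816.

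- Difference: 0.125 − 0.028 = 0.097; squared, 0.009409.
- Sum of variances: 0.125 × 0.875 + 0.028 × 0.972 = 0.109375 + 0.027216 = 0.136591; square root 0.3696.
- Unpooled formula: n = (1.960 + 1.2816)² × 0.136591 / 0.009409 = 152.5 per arm.
- Pooled formula: mean rate 0.0765, so 2 × 0.0765 × 0.9235 = 0.141296; square root 0.3759. Then n = (1.960 × 0.3759 + 1.2816 × 0.3696)² / 0.009409 = 155.7 per arm.

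The stated 154 lies between the two. A one-sided test would need only 124.3 (unpooled) to 127 (pooled), which supports the two-sided assumption. The stated figure follows from transfusion rates alone; blood loss plays no part in it.

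**Power at the planned 200 per arm, two-sided 0.05.**

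- Pooled: (0.097 × √200 − 1.960 × 0.3759) / 0.3696 = (1.3718 − 0.7367) / 0.3696 = 1.718, giving 95.7%.
- Unpooled: 1.3718 / 0.3696 − 1.960 = 1.752, giving 96.0%.

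**Error rate under each reading.**

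- Transfusion alone, as section 12 states: 5%.
- Both outcomes required: at most 5%.
- Either outcome sufficient: 1 − 0.95² = 9.75% if the two tests were independent, and less if they are correlated (about 9.1% at an assumed correlation of 0.5 and 7.0% at 0.9). The documents give no correlation.

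Only the third reading inflates the error. No sentence in the plan states it, and the objective joins the two measures with *and*, not *or*.

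**The case for a change.** The strongest case for acting is that the objective sentence is more than a general aim: it names the measures by which effectiveness will be judged, and the only secondary objective given is cost. The planning rates come from one small study with 32 and 35 patients in these arms, which by the plan's own account found no significant difference between the drugs. A non-significant transfusion result is therefore quite possible, and that is when loose wording might be exploited. Rewording would be nearly free.

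The mismatch itself stands: the opening section and section 12 do not say the same thing. It does not stand that the ranking is left open, because section 12 gives it in consecutive sentences. Nor is the opening section a full list of endpoints: change in hemoglobin is a secondary endpoint in section 12 and appears in none of the stated objectives. An objective may also draw on a primary and a secondary endpoint together. A report that promoted blood loss to the primary result would contradict section 12 outright, and anyone holding the protocol could see that.

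**Conclusion.** This is a clerical inconsistency between an introductory sentence and the statistical section. An analyst following section 12 tests transfusion as the single primary endpoint and reports blood loss as secondary, which is also what the hypothesis and the sample size assume. Aligning the wording would alter no analysis: 154 per arm stands, power at 200 per arm stays at 95.7% to 96.0%, and the primary error rate stays at 5%. These figures rest on the plan's own transfusion rates and on a two-sided test, which is inferred rather than stated. The inflated error rates depend on an either-suffices rule found nowhere in the plan, so they do not describe this trial. No change is called for.

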All data needed for this study including blood loss, need for transfusion, preoperative and lowest postoperative hematocrit and hemoglobin, and complications will be collected during the hospitalization. Subject's study participation will end at hospital discharge. Costs of each component of the hospital stay will also be obtained and recorded. Adverse events will be recorded on case report form and submitted to the Duke IRB per Adverse Event policy.

The recruitment goal of this study is to enroll 75% of eligible subjects electing to undergo either primary hip or knee arthroplasty performed by three attending surgeons at this institution over a year time period.

5. Selection of Subjects

Adult patients aged 18 and over electing to undergo primary total hip or knee arthroplasty will be considered for inclusion in the proposed study and identified preoperatively.

6. Subject Identification, recruitment, and compensation

Adult patients aged 18 and over electing to undergo primary total hip or knee arthroplasty will be considered for inclusion in the proposed study and identified preoperatively. Exclusion criteria will include history of stents, MI, CVA, DVT, PE,

color blindness, and hypercoagulable state. Females of childbearing age will also have a serum pregnancy test drawn before inclusion in this study. A positive pregnancy will result in exclusion from the study. We aim to recruit 400 subjects, 200 total hip and 200 total knees. Subjects may withdraw at anytime. Post operatively, surgery data will be collected via the electronic medical record. Consent will be signed and witnessed before surgery takes place in clinic.

7. Consent Process

The investigator or his/her authorized designee will inform the subject of all aspects pertaining to the subject's participation in the study during the consent process. The process of obtaining informed consent will be in accordance with all applicable regulatory requirements (Federal Register Vol. 48, No. 17, 1982, pp 8951-2).

8. Subject's Capacity to Give Legally Effective Consent

Each patient aged 18 years or older will consent for him or herself. If the patient is less than 18 years of age they will not be considered for the study.

9. Study Interventions

Subjects will be randomly assigned in a 1:1 ratio to either an Amicar or TXA arm which are both standard of care at Duke. Subject's study participation will end at hospital discharge.

10. Risk/Benefit Assessment

Potential Benefits: Despite being off-label, TXA and Amicar are already both being used across various fields, including orthopaedics, for their benefit in reducing blood loss, the need for transfusion, and a drop in hemoglobin during major surgery and have shown to be safe to use.^{1,14,15} Patients given TXA or Amicar will likely experience decreased blood loss and decreased risk of transfusion and as a result may experience shorter hospital stay, fewer complications and decreased cost. Both are currently used as standard of care in total hip and knee replacements.

Potential risks: Although initially there was a fear that TXA or EACA would increase the risk of death and thromboembolic events, current evidence suggests that this increase is not statistically significant.⁸ TXA is currently used as the standard of care at Duke University Hospital.

However, subjects in the TXA arm may experience the following adverse effects including GI disturbances (nausea, vomiting, diarrhea), allergic dermatitis, giddiness, and hypotension. The FDA also lists the risk of serious rare side effects including thromboembolic events (such as deep vein thrombosis, pulmonary embolism, cerebral thrombosis, acute renal cortical necrosis, and central retinal artery and vein obstruction), convulsion, chromatopsia, and visual impairment.

Adverse effects associated with Amicar include edema, headache, malaise, hypersensitivity (anaphylaxis), cardiovascular effects (bradycardia, hypotension, peripheral ischemia, thrombosis), GI disturbances (abdominal pain, diarrhea, nausea, vomiting), hematologic effects (agranulocytosis, coagulation disorder, leukopenia, thrombocytopenia), musculoskeletal effects (CPK increase, muscle weakness, myalgia, myopathy, myositis, rhabdomylolysis), neurologic complications convulsions. delirium, dizziness. hallucinations. (confusion, hypertension, stroke, and syncope), respiratory effects (dyspnea, nasal congestion, pulmonary embolism), rash, pruritis, tinnitus, decreased vision, watery eyes, and urogenital effects (increased BUN and renal failure). Amicar is less potent than TXA so it may lead to increased blood loss and therefore increased risk of transfusion according to one study.1

Many of the above side effects for both TXA and Amicar have been reported in patients with hemophilia.

11. Costs to the Subject:

Subject or *their* insurance provider will be responsible for all costs related to your medical care, including the drugs used in this study.

No direct monetary compensation will be offered for inclusion in the proposed study.

12. Data Analysis & Statistical Considerations

Subject characteristics and study results including those outlined above (considered complications or adverse events) will be recorded. ¹ The primary endpoint for this study is the percentage of patients requiring transfusions. The secondary endpoint include total blood loss (recorded as estimated blood loss intraoperatively as determined by anesthesia staff, and postoperatively recorded by nurses from the output in drains), change in hemoglobin (preoperative vs. postoperative hemoglobin that is routinely measured before discharge), and the total cost of hospitalization as billed by Duke University (including pharmacy cost, price each night in hospitalization, all other charges incurred during admission). Binary variable results will be compared using chi-square and Fisher's exact tests (where appropriate). We plan a comparison of continuous variable results using Wilcoxon rank sum and t-tests (where appropriate). We will consider multivariable logistic regression in determination of TXA and Amicar and their correlation with the above listed complications and adverse events. Anesthetic techniques will be recorded for analysis and covariate analysis will be performed at the end of the study. In order to perform a cost analysis, total cost of hospitalization including pharmacy cost, potential transfusion costs, and cost of stay. Based on the one small European study, sample size for finding the difference between two proportions was calculated using a proportion of 0.125 patients given Amicar were transfused (n=32 vs. 0.028 (n=35) given TXA. Using an alpha value of .05 and power of .90 it was determined that there would need to be 154 patients in each sample size to find a significant difference in independent samples. Our goal of enrolling 400 patients total (200 in each arm) will therefore be appropriate for this study

13. Data & Safety Monitoring

The primary investigator will collect data from the subject's electronic medical record and will extract necessary study data and then transfer this data into a limited access electronic Excel spreadsheet housed on the Duke Orthopaedic share drive. We will have an independent safety reviewer in lieu of a formal DSMB committee to ensure the safety of subjects. [name], head of the orthopaedic clinical research unit will be asked to serve in this role. He will review available safety data, including thrombotic complications after 100, 200, and 300 patients are enrolled.

During collection, data will be indexed by the subject's medical record number. After data collection, a case number will be assigned to the data, and the medical record number, name and any dates associated with clinical care (the only identifying data collected) will be stripped from the database. The code linking medical record number to case number will be kept in an Excel spreadsheet with access limited to the primary investigator and his research team. Electronic research records will be stored on a DHTS server in the following limited access folder O:\CLINICAL RESEARCH DATA\JOINT\50108 - [name] TXA vs. Amicar. Paper research documents will be stored in the PI's locked research office in a locked cabinet with keys in possession of the CRC. Paper documents will be housed in the PI's locked research office in a locked cabinet with access limited to his research team and keys in possession of the CRC. When the study is complete, the code linking medical record numbers to case numbers will be destroyed. During data collection and review, protected health information will be available only to the primary investigator and will not be reused or disclosed to any other person or entity, except as required by law, for authorized oversight of the research study.

14. Privacy, Data Storage & Confidentiality

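### Section 12 does not say which postoperative hemoglobin defines the change endpoint; if it is a late value, transfusion masks part of the between-arm difference

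*Combined protocol and SAP*

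**What the plan says.** Section 12 (Data Analysis & Statistical Considerations) defines the endpoint as "change in hemoglobin (preoperative vs. postoperative hemoglobin that is routinely measured before discharge". It names no day and gives no first, last or lowest rule.

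Section 4 (Study Design) lists what is collected during the hospital stay, including "need for transfusion, preoperative and lowest postoperative hematocrit and hemoglobin". No section says what to do with a hemoglobin value taken after a transfusion.

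Transfusion is expected to differ by arm. The opening section hypothesizes that "TXA will decrease the transfusion rate in patients as compared to Amicar", and the sample size in Section 12 uses "a proportion of 0.125 patients given Amicar were transfused (n=32 vs. 0.028 (n=35) given TXA".

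On the test, Section 12 says "We plan a comparison of continuous variable results using Wilcoxon rank sum and t-tests (where appropriate". After mentioning anesthetic technique it adds that "covariate analysis will be performed at the end of the study", without naming preoperative hemoglobin or the joint operated on.

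**The concern.** A patient with several inpatient draws has several possible changes in hemoglobin, so two analysts following Section 12 could compute different endpoints from the same charts. The choice could also be made after the data are seen.

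The choice matters because transfusion raises hemoglobin and is itself the primary endpoint. In a value drawn after transfusion, part of the drop is hidden. Under the trial's hypothesis this happens in more Amicar than TXA patients, so the arms look more alike than the bleeding was.

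A lesser and separate matter is precision. The stated comparison is unadjusted, although preoperative hemoglobin and joint are both known for every patient.

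**Working it through.** **Inputs from the documents.** Transfusion rates 0.125 (Amicar) and 0.028 (TXA), alpha 0.05, power 0.90, 154 per arm required and 200 per arm planned (all Section 12).

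**Assumptions.** The documents give no SD, rise per transfused patient, transfusion trigger or draw schedule. I take a rise of 1 or 2 g/dL and an SD of 1.2 g/dL for the drop.

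1. *The plan's own figure.* Two-sided, unpooled: (1.960 + 1.282)² × (0.125 × 0.875 + 0.028 × 0.972) / 0.097² = 152.5, so 153 per arm. The pooled formula gives 156. The stated 154 is reproduced closely enough for the rates to be used as inputs.

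2. *Patients affected.* 200 × 0.125 = 25 on Amicar; 200 × 0.028 = 5.6 on TXA; about 31 of 400 in all.

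3. *Masking in a late sample.* Shift = (0.125 − 0.028) × rise = 0.097 g/dL for a rise of 1 and 0.194 g/dL for a rise of 2. This takes the sample to follow every transfusion.

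4. *Relative size.* If transfusion follows a drop beyond one common cut-off and drops are normal, the planning rates imply a true difference of 1.2 × (1.911 − 1.150) = 0.913 g/dL. The shift is then 0.097 / 0.913 = 10.6% or 0.194 / 0.913 = 21.2% of it.

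5. *Power.* The standard error is 1.2 × √(2/200) = 0.12 g/dL. The difference is 0.913 / 0.12 = 7.6 standard errors unmasked, and (0.913 − 0.194) / 0.12 = 6.0 with the larger shift. Power is near 100% either way.

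6. *What the lowest value recovers.* This was simulated with 2,000,000 patients per arm: draws on days 1 to 3 at 70/90/100% of the full drop, SD of the full drop 1.16, measurement SD 0.3, planning rates. The late sample gives a difference of 0.799 (rise 1) or 0.702 (rise 2), so the common unmasked difference is 0.799 + 0.097 = 0.896.
   - No transfusion before the first postoperative draw: the lowest value gives 0.856 or 0.854. The shortfall falls from 0.097 to 0.040 (59% removed) or from 0.194 to 0.042 (78% removed). A repeat simulation, with a true difference of about 0.905, gave about 40% and 70%.
   - A quarter transfused before that draw: the lowest value gives 0.839 or 0.811. The shortfalls are 0.057 (41% removed) and 0.085 (56% removed).
   - All transfused before that draw: no gain. The lowest value is slightly worse than the late one, because measurement noise compresses a lowest-of-three difference (about 0.865 against 0.90 even without transfusion).

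7. *Dependence on draw frequency.* The expected minima of 3 and 5 standard normal draws are −0.847 and −1.163. Two extra draws in every Amicar patient at a flat level would inflate the difference by 0.3 × 0.316 = 0.095 g/dL. Two extra draws in transfused patients only change it by less than 0.01 g/dL.

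8. *ANCOVA against the unadjusted change score.* With equal pre and post variances the variance ratio is (1 − ρ²) / (2(1 − ρ)). At ρ = 0.5 this is 0.75 / 1.0 = 0.75; at ρ = 0.8 it is 0.36 / 0.4 = 0.90. The variance is 10 to 25% lower.

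**The case against.** The strongest reply is that the sections do not conflict. Participation ends at discharge, so every inpatient value is a pre-discharge value. Section 4 presents its list as complete for the study, and the only postoperative hemoglobin in it is the lowest. That reading is natural, and a reader who infers a flat contradiction goes further than the text. What stands is that Section 12 does not say so and leaves a late value open.

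Nor do the documents show that a late sample is intended. The opening section mentions a day-5 hemoglobin result, but as background on the prior European trial; this protocol adopts no day.

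The shift is bias only if the target is hemoglobin loss from bleeding. Hemoglobin at discharge whatever was transfused would be a legitimate target, and the plan names neither. Transfusion and total blood loss are also endpoints in their own right, so bleeding masked here is still captured elsewhere. This limits the damage but does not define the endpoint.

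A reader might infer lost significance. At the planning rates there is none. Power moves only if the true difference is much smaller: at an assumed 0.4 g/dL (2 in 25 or fewer transfused on TXA, at 6.9%), it goes from 91–92% to 77–90% on a late sample. That case leaves the plan's own rates.

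Finally, the lowest value is not a clean correction. It can follow an early transfusion, and unequal draw frequency could push the difference the other way. Both points stand.

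**Conclusion.** The point holds as a gap in specification with a conditional and modest consequence. Section 12 needs to name the sample and the handling of transfused patients. If a late value were used and bleeding-related loss is the target, the difference would be understated by about 0.10 to 0.19 g/dL at the planning rates, for assumed rises of 1 to 2 g/dL. That is roughly 11 to 21% of the difference those rates imply at an assumed SD of 1.2 g/dL.

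The shift is toward no difference, so it cannot create a TXA benefit. The documents do not support any inference that the primary endpoint or its sample size is compromised.

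The covariate point is separate. It concerns precision only, and adjusting for preoperative hemoglobin does nothing about the masking.

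**What to change.** In Section 12:

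1. Define change in hemoglobin as the preoperative value minus the lowest postoperative value before discharge, as collected under Section 4, with transfused patients included at their lowest recorded value. Acknowledge that this reduces masking without removing it and that the lowest value depends somewhat on how often blood is drawn. If hemoglobin at discharge regardless of transfusion is the intended target, state that instead.

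2. Make ANCOVA with arm, preoperative hemoglobin and joint (hip or knee) the main analysis of this endpoint, and keep the Wilcoxon test as a check.

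3. Optionally, record the number of units given before the lowest sample and run a sensitivity analysis over a stated range of rise per unit. This has to be done before the step in Section 13 at which "any dates associated with clinical care (the only identifying data collected) will be stripped from the database", because timing cannot be worked out from the database afterwards.

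Items 1 and 2 cost only wording: Section 4 already collects "preoperative and lowest postoperative hematocrit and hemoglobin", and the joint is known. Item 3 adds one field, needed in about 31 of 400 charts at the planning rates.

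### The cost endpoint is the billed total, so unequal departmental mark-ups could distort a comparison that the hypothesis frames as cost

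*Combined protocol and SAP*

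**What the plan says.** Section 12 lists cost among the secondary endpoints and defines it as "total cost of hospitalization as billed by Duke University (including pharmacy cost, price each night in hospitalization, all other charges incurred during admission". Further on, the same section adds: "In order to perform a cost analysis, total cost of hospitalization including pharmacy cost, potential transfusion costs, and cost of stay". That sentence has no main verb and does not say how the items are to be valued.

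Section 4 states: "Costs of each component of the hospital stay will also be obtained and recorded". It does not say whether these are resource costs from hospital accounts or lines of the bill.

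The opening section, before Section 3, sets the question. The objective reads: "A secondary objective is to determine the overall cost of hospitalization when the two different products are used". The hypothesis reads: "We also hypothesize that the overall cost of hospitalization will be less in patients with TXA, despite the increased pharmacy cost". The supporting figures are "TXA currently costs between \$100-200 per each IV dose" and "A unit of RBC costs between \$500-1000 dollars", together with the remark that "Amicar is significantly less expensive than TXA", for which no price is given. The same section cites a study of knee replacement with and without TXA, in which pharmacy cost rose by $140 and total hospital cost fell by about $900.

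The document gives no costing perspective, no conversion from charges to costs, and no sensitivity analysis on valuation.

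**The concern.** The hypothesis describes a trade: a dearer drug is to be paid for by less blood and less hospital use. Whether the trade comes out ahead depends on the relative prices put on those items. A bill prices each item at cost times a mark-up, and mark-ups may differ between pharmacy, blood bank and ward. If they are all equal, billing only rescales the arm difference. If they are unequal, the drug and the offsetting savings are weighted differently from their costs, and the difference in charges can depart from the difference in cost in size and, when the two sides nearly balance, in sign.

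As written, the endpoint therefore answers a question about charges at one hospital, while the opening section argues about cost to inform a choice of agent that many hospitals face. This concerns what is measured, not which test or summary statistic is used.

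**Working it through.** **The plan's own figure.** No number is given for the cost endpoint. The transfusion rates used below come from the sample size calculation in Section 12, which reproduces. With p1 = 0.125, p2 = 0.028, power 0.90 and alpha 0.05 (taken as two-sided, since sidedness is not stated), the pooled formula without continuity correction gives 156 per arm. The unpooled formula gives (1.960 + 1.282)² × (0.125×0.875 + 0.028×0.972) / 0.097² = 152.5, so 153. The plan states 154.

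**Inputs from the documents.** Transfusion rates 0.125 (Amicar) and 0.028 (TXA); red cells $500-1000 per unit; TXA $100-200 per dose.

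**Assumptions.**
- Units per transfused patient, u: 1 to 2.
- Extra drug cost of TXA over Amicar, E: $100 to $200. Neither an Amicar price nor the number of doses is given, so the true value may lie outside this range.
- Mark-ups m_drug and m_blood: unknown.

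**Formulas, per patient, TXA minus Amicar.**
- Blood saving B = (0.125 − 0.028) × u × price = 0.097 × u × price.
- Net at cost = E − B.
- Net as billed = m_drug × E − m_blood × B.
- The billed net is zero when m_drug / m_blood = B / E (the flip ratio). Above it TXA looks dearer; below it TXA looks cheaper.

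| Units × price | B | Net at cost, E = $100 / $150 / $200 | Flip ratio B/E, E = $100 / $150 / $200 |
|---|---|---|---|
| 1 × $500 | $48.5 | +51.5 / +101.5 / +151.5 | 0.485 / 0.32 / 0.24 |
| 1 × $1000 or 2 × $500 | $97 | +3 / +53 / +103 | 0.97 / 0.65 / 0.485 |
| 2 × $750 | $145.5 | −45.5 / +4.5 / +54.5 | 1.46 / 0.97 / 0.73 |
| 2 × $1000 | $194 | −94 / −44 / +6 | 1.94 / 1.29 / 0.97 |

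The flip ratios straddle 1, so drug and blood are of similar size and unequal mark-ups can matter in either direction. Two illustrations with assumed mark-ups:
- E = $100, 2 units at $750. At cost, 100 − 145.5 = −$45.5 (TXA cheaper). With drug marked up 4 times and blood 2 times, 400 − 291 = +$109 (TXA dearer).
- E = $150, 1 unit at $1000. At cost, 150 − 97 = +$53 (TXA dearer). With drug marked up 2 times and blood 4 times, 300 − 388 = −$88 (TXA cheaper).

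With equal mark-ups k, the billed net is k(E − B), and the sign never changes.

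**Limits of the arithmetic.**
- It omits stay and all other items. In the cited study the non-pharmacy saving is 900 + 140 = $1,040 against $140 of pharmacy cost. If that applied here, with one common mark-up on everything outside pharmacy, the flip ratio would be 1,040/140 = 7.4.
- A smaller E also makes it harder to turn a TXA saving into an apparent loss: at E = $50 and B = $194 the ratio is 194/50 = 3.9.
- With 200 per arm, the standard error of a difference in means is SD × √(2/200) = 0.1 × SD. At an assumed SD of $1,000 for admission cost it is $100, so a true difference of $45.5 is about half a standard error. A larger SD raises the standard error in proportion.

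**The case against.** The strongest reply is that the billed total is a disclosed and legitimate choice. Section 11 makes the subject or the insurer responsible for the cost of care, so a payer's view is not plainly wrong. The opening section does not say whether its drug and blood prices are acquisition costs or charges. This stands in part: the documents do not show that charges are the wrong quantity, only that the perspective is unstated and that the argument is put in terms of cost.

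Three stronger readings are tempting, and the documents do not support them.

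- *A reader might infer that the plan contradicts itself by collecting component costs in Section 4 and then choosing charges in Section 12.* Section 4 gives no valuation basis, and Section 12 mixes the words cost, price and charges in one definition. The components may simply be bill lines.
- *A reader might infer that the trial will name the wrong drug as cheaper.* Every mark-up above is assumed, and nothing shows that this hospital's mark-ups differ. Savings on stay could outweigh the drug-plus-blood balance, and at this sample size chance alone could give either sign on either valuation. Nor does the cited $140 bound the extra cost of TXA over Amicar: it compares TXA with no TXA, and the plan gives up to $200 per dose with no dose count.
- *A reader might infer that including every other charge biases the comparison.* The hypothesis is about the whole admission, so an all-inclusive total fits it. Under 1:1 randomisation, items the drug does not affect add variance, not bias. The later sentence in Section 12 names three items as included in the total and does not restrict the total to them.

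**Conclusion.** The concern holds as a weakness of measurement. The endpoint as written estimates a difference in billed charges, which need not track the difference in cost that the hypothesis is about. On the plan's transfusion rates and red-cell price, with 1-2 units per transfused patient and $100-200 of extra drug cost assumed, drug and blood come close to offsetting each other. Unequal mark-ups could then change the sign of that component. Reversal of the whole total is possible but not demonstrated, and becomes unlikely if stay and other savings are large.

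The matter is confined to one secondary endpoint, though that endpoint carries one of the trial's two stated hypotheses. It is a worthwhile, inexpensive improvement, not a threat to the main result.

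**What to change.** In Section 12:

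1. State the costing perspective, and state whether the component costs in Section 4 come from hospital cost accounts or from the bill.
2. Define the endpoint as hospital cost per admission, summed from components. Where only a charge exists, convert it with the department-level cost-to-charge ratio. If the Section 4 components prove to be bill lines, this step is essential, because summing them unconverted only returns the billed total.
3. Report two quantities: total admission cost, which answers the hypothesis, and the subtotal for pharmacy, transfusion and stay, which removes variance from items the drug cannot affect.
4. Keep billed charges as a sensitivity analysis.
5. Complete the unfinished cost-analysis sentence accordingly, before the cost data are examined, so that the valuation basis is not chosen after seeing results.

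The cost is a short rewrite and a request to hospital finance for component costs or conversion ratios. Nothing changes for patients.
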